7.1.1. Site visits

Visit 0 (Inclusion visit)

If a potential subject is interested in participating after the first contact, a visit (visit 0) will be arranged in a room reserved to ensure privacy and quiet surroundings at the investigators clinic/department. When arranging the visit, it will be ensured, that the subject has received the Subject Information Form prior to the visit. The subjects will receive both written and verbal information to ensure that the subject understands what was read and explained and can freely agree to participate in the investigation. The subject will, beforehand, also be informed about the possibility of bringing a companion to Visit 0 and to any possible subsequent visits. During the visit the principal Investigator, or delegate, will provide oral information about the investigation based on the Subject Information Form. The subject has the right to wait before deciding on participation.

If/when subjects decide to participate, they will be asked to sign the Informed Consent Signature Form. Hereafter, relevant female subjects will be asked to give a urine sample for a pregnancy test. The sample will be destroyed right after the test. If a subject so desires, and it is certain that it is understood what the investigation entails, and the relevant form has been signed the subjects are considered enrolled in the investigation. Enrolled subjects that are deemed eligible per the inclusion/exclusion criteria are allocated a subject number.

Visit 0 and visit 1 can be combined.

Test visits (V1, V2 and V3)

During test visit 1, the subject will be randomised to either treatment Arm A or Arm B and will be allocated a randomisation number. Hereafter the baseline questions will be completed by the Principal Investigator, or delegate. The subjects will be introduced to the clinical trial app and how to complete the questionnaires and take photos.

At test visit 1 and 2 investigational products (CE marked comparator products or non-CE marked Investigational Product) will be handed out according to the randomisation. The subject will only be informed about which product to wear in the upcoming period. At the visits the subjects will be trained according to the IFU, in preparation of the product (e.g. hole size), preparation of skin before application (e.g. cleaning and wiping), application of the product (e.g. correct position and applying pressure to the baseplate), removal of product and storage of the product.

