At each test visit the Principal Investigator, or delegate, will assess the skin and complete questionnaires about the subject's peristomal skin condition and ask the subject about stoma behaviour since last visit/call. The

CONFIDENTIAL

subject will, at each test visit, complete questionnaires about e.g. skin condition, stoma behaviour, leakage and quality of life. Additionally, the principal investigator, or delegate, will take a photo of the peristomal skin, for assessment of changes in peristomal skin condition from Test visit 1 to Test visit 2, and from test visit 2 to test visit 3.

At test visit 2 and 3 the Principal Investigator, or delegate, will also complete questionnaires about changes in peristomal skin condition. The subject will also complete questionnaires about changes in peristomal skin conditions, feeling of security and handling of the product.

It must be ensured that the subject sits alone in a room reserved to ensure privacy and quiet surroundings and is not disturbed when the completing the questionnaires at the visit.

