In light of the data obtained it might be considered to make additional explorative analyses based on a subset of the ITT/PP population.

Analysis of the primary endpoint

Max itching score within a week at steady state will be analysed by a mixed repeated measures model using individual week max scores (on a scale from 0-10) as the observational unit. The model will consider that observations corresponding to different subjects are independent; whereas observations corresponding to the same subject are correlated. The correlation between observations corresponding to the same product can be larger than observations corresponding to different products. Hence the model includes a fixed effect of product (comparator product, test product), a fixed effect of product type (1- or 2-pc), a fixed interaction between product and product type, a fixed period effect, an interaction between period and product, a random effect of subject and a random interaction effect of product and subject.

The model might be reduced by removing non-significant fixed effects, if relevant. The interaction between period and product allows for a possible carry-over effect. It is assumed that a possible carry-over effect is the

CONFIDENTIAL

same for 1- and 2-pc users. If the interaction is significant, data from only the first test period will be analysed as a parallel arm study because the first period is free of carry-over effects and period will be excluded from the model.

All combinations of differences between the two products will be estimated for both 1- and 2- pc products. Furthermore, differences for same product between product types will be estimated (if the model is not reduced).

Analysis of the secondary endpoints

The endpoints regarding pain, burning, physical discomfort, ability to move around and the overall ability to stick the baseplate to the skin (on a scale from 0-10) will be analysed by the same model as the primary endpoint starting by calculating the max within a week at steady state.

[REDACTED] endpoints regarding bleeding (Y/N), experiencing any weeping or moisture (Y/N) and Ulcers or sores (Y/N) per baseplate change at steady state will be analysed by a repeated logistic regression model with the same effects included as for the primary endpoint.

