The total DET score from Visit 2 and 3 will be analysed by a linear mixed model similar to the model for the primary endpoint, except that the random interaction effect of product and subject is not included, as there is only one measurement per subject for each product. The endpoints regarding individual item scores (discoloration, erosion and tissue overgrowth) can be analysed by the same model, if relevant.

The discoloration area and intensity at steady state will be analysed by the same model as described for the primary endpoint. For these analyses the data from the individual skin photos are the observational unit.

The endpoints regarding frequency in the past 14 days by end of treatment (of itching, pain and burning) will be analysed similar to the analysis of total DET score. Instead of a mixed model, a generalized linear mixed model, namely a proportional odds model, will be applied for the analysis as the response is on a 5-point scale. Proc Glimmix will be applied for the analysis.

Analyses of exploratory endpoints

The leakage area and leakage diameter at steady state will be analyzed by the same model as the discoloration area and intensity described under secondary endpoints.

The median wear time will be analyzed by the same model as the total DET score. The median wear time per subject is based on data from the 3 last weeks in each period.

The three scores from the leakage scale questionnaire (emotional impact, usual/social activities, coping/control) as well as the total score and the sub-scores (discreteness, comfort, confidence and social life) from the quality of life questionnaire will be analyzed by the same model as the total DET score.

The endpoint regarding feeling of security as well as the 3 endpoints regarding handling will be analyzed by the same proportional odds model as described for the frequency of itching in the past 14 days by end of treatment.

The proportion of subjects preferring test product will be compared with the proportion preferring the comparator by a test in the binomial distribution, testing the hypothesis that the proportions are equal.

Analyses of safety endpoints

Adverse events will be listed and summarized, if relevant.

CONFIDENTIAL

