11.2. Sample size

The itching score is given at each baseplate change and the max of these scores per week at steady state is the primary endpoint. The max score is only calculated if there are measurement for more than four days within a week. For each subject approximately three measurements will be available for each test period.

The sample size calculation is based on a simplified linear mixed model with only 1-pc users and no period effect (corresponding to the design from CP300). The model includes a fixed effect of product (comparator and test product), a random effect of subject and a random interaction effect of product and subject.

Based on data from CP300 it is assumed that the total standard deviation of the primary endpoint is 1.82 and that the total variation 1.82² is divided so that:

- a random effect of subject accounts for 68% of the total variation
- a random interaction effect of product and subject accounts for 0%
- and the residual accounts for 32% of the total variation

In table 1 the needed sample size is calculated by simulation for varying values of the true difference between comparator and test product regarding mean max itching score per week and for different values of the power to demonstrate that the difference is significantly different from 0.

Table 4: Subjects needed for comparing mean max itching score between two products

True difference	Reduction in mean if the mean for the comparator is 2.2 as for [REDACTED] in CP300	Power		
		0.8	0.85	0.9
0.6	27%	46	>46	>46
0.7	32%	35	40	45
0.8	36%	30	32	36

Based on the numbers in the table, 40 subjects should test each product to ensure a power of 85%, if the true difference between the comparator product and a test product is 0.7 (corresponding to a 32% reduction if the mean for the comparator is 2.2 as in CP300). This will be enough when comparing the two products. 1-pc and 2-pc users will be evaluated separately (in a combined model). As there are no previous data for 2-pc users the sample size calculations for 1-pc users is assumed to cover 2-pc users as well. To take a potential drop-out (20%) into account it is recommended to include a total of 48 1-pc and 48 2-pc users, resulting in a total of 96 subjects.

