11.3. Level of significance and power

A significance level of 5% will be applied. For a description of the power see section 11.2 above.

CONFIDENTIAL

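### The baseline questions follow randomisation in an open-label trial, and the first-period-only fallback leaves the visit 1 DET and quality-of-life scores unused as covariates

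*Combined protocol and SAP*

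**What the plan says.** **Order of steps.** Section 7.1.1 (test visits) places randomisation to Arm A or B at V1, followed by: "Hereafter the baseline questions will be completed by the Principal Investigator, or delegate". Section 4.6 states that there is no blinding. Appendix 4 lists the name or type of the randomised product among the baseline data.

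**Other V1 data.** Section 7.1.1 also has the investigator assess the skin at each test visit and the subject complete questionnaires on skin, leakage and quality of life. A photo is taken "for assessment of changes in peristomal skin condition from Test visit 1 to Test visit 2", and likewise for the next interval. No order relative to randomisation is given for these. Appendix 1 marks DET items and the quality-of-life questionnaire at V1, as far as the table can be read.

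**Analysis.** Section 11.1 summarises or lists baseline data. The primary model has product, product type, period, two interactions and random effects, with no baseline term. For the investigator-graded skin score, "The total DET score from Visit 2 and 3 will be analysed by a linear mixed model", so V1 is not used. If the period-by-product interaction is significant, "data from only the first test period will be analysed as a parallel arm study". The only change to the model then stated is that period is dropped.

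**Fallback power.** Section 11.2 gives 82% for a difference of 1.7 with 20 per arm, and 83% for 1.2 with 40 per arm.

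**The concern.** Two things are at issue.

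First, a baseline taken after allocation in an open-label trial is not protected from being coloured by it. Date of birth is hardly at risk, but recalled frequency of skin complications, a graded skin assessment or a subject's questionnaire could be. A value that is to serve as a covariate or as a reference for change should be recorded before allocation.

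Second, the fallback changes the kind of comparison. In the cross-over each subject is their own control. In the first-period analysis the product contrast lies between subjects, where the plan's own variance split puts most of the variation: "a random effect of subject accounts for 68% of the total variation". A V1 value of the same measure would explain part of that, and for DET and quality of life it is already being collected. At stake is precision in an analysis that has little to spare.

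**Working it through.** **Inputs.** Section 11.3: "A significance level of 5% will be applied". Section 11.2 describes the target as "the power to demonstrate that the difference is significantly different from 0", taken here as two-sided. Section 11.2 also assumes that "the total standard deviation of the primary endpoint is 1.82", with 68% of the variance between subjects, 0% for product by subject and 32% residual. The fallback cases are 20 per arm at 1.7 and 40 per arm at 1.2. The correlation r between a V1 covariate and the outcome is not in the documents; it is an assumption and is varied.

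**Step 1: reproduce the plan's figures.** Two-sample t-test, noncentrality = difference / (SD × √(2/n)), df = 2n − 2.

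- 20 per arm: 1.7 / (1.82 × √0.10) = 1.7 / 0.576 = 2.95, df 38. Power 82.1% (plan: 82%).
- 40 per arm: 1.2 / (1.82 × √0.05) = 1.2 / 0.407 = 2.95, df 78. Power 83.0% (plan: 83%).

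The stated powers are therefore those of an unadjusted comparison.

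**Step 2: complete-data cross-over.** A single V1 value per subject is the same in both periods. It cancels from the within-subject product difference, so adjustment adds essentially nothing there.

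**Step 3: fallback with a covariate, weekly maximum itching.** Residual SD = 1.82 × √(1 − r²), with one further degree of freedom spent (df 37 and 77).

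| Assumed r | Variance removed (r²) | Residual SD | Power, 1.7, 20/arm | Power, 1.2, 40/arm |
|---|---|---|---|---|
| none | 0% | 1.82 | 82% | 83% |
| 0.1 | 1% | 1.81 | 82% | 83% |
| 0.2 | 4% | 1.78 | 84% | 84% |
| 0.3 | 9% | 1.74 | 85% | 86% |
| 0.5 | 25% | 1.58 | 91% | 92% |

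**Step 4: which r is plausible?** The 0–10 itching score is given at each baseplate change, and Appendix 1 shows no legible V1 score on that scale. The covariate would have to be the closest V1 skin item, such as DET, recorded while the subject arrives on the usual product. The lower rows are the safer expectation.

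**Step 5: DET, quality of life and leakage.** Here the covariate can be the same measure, so r may well be higher. The documents give no SD or target difference for these endpoints, so no power figure can be supported.

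**Step 6: how scarce precision is.** At the cross-over design difference of 0.7, the unadjusted fallback has power of 22% with 20 per arm and 40% with 40 per arm (same formula, noncentrality 0.7/0.576 = 1.22 and 0.7/0.407 = 1.72).

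**The case against.** **Do the late baseline data bias the results?** A reader might infer so. The documents do not support it. That the assessor has seen the arm is a reasonable inference from the order of steps, the open label and the randomised product being a baseline item, but it is not stated, and product hand-out is described after the baseline questions. The sentence on order concerns the baseline questions of Appendix 4, which do not include DET or quality of life. For the skin assessment, questionnaires and photo no order is given. Values that enter no visible model also cannot bias the contrasts from those models. The photo is a reference for change, but no legible analysis in section 11.1 uses that change. What stands is that the order is unprotected, and that it must be fixed if V1 values become covariates.

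**Is the gain as large as r = 0.68 would imply?** The formula in the working would then give about 98% power in both cases. But 0.68 is the between-subject share for repeated itching scores on one scale. It is not a correlation between a V1 skin grade and later self-reported itching, so 98% should not be expected.

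**Is the starting power conservative?** Yes. The 82% and 83% fit one score per period, while about three weekly maxima are expected. Averaging three gives SD 1.82 × √(0.68 + 0.32/3) = 1.61 and unadjusted power of about 90% and 91%, so the room for improvement at those differences is smaller than the table suggests.

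**Is chance imbalance left as an error?** No. Under randomisation the unadjusted standard error already covers it. Adjustment is about precision.

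**Does this address the fallback's main weakness?** No. A simulation with no product or carry-over effect and one score per period shows that, once the carry-over test triggers the fallback, the unadjusted first-period test is significant in about 62–64% of cases, with overall type I error near 8%. With adjustment at an optimistic r of 0.68, in the carry-over test as well, these are still about 47% and 7%. The powers in the table are unconditional and do not describe the two-stage procedure.

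**Conclusion.** The point holds as a free improvement of modest size. The baseline questions follow randomisation in an open-label trial, and no text secures the other V1 assessments before allocation is known. No visible model uses a V1 value. This is harmless in the complete-data cross-over but gives up precision in the first-period-only analysis.

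For weekly maximum itching, the stated 82% and 83% move to between 82% and 91%, and between 83% and 92%, over assumed correlations of 0.1 to 0.5. At 0.1 to 0.2 the gain is at most about two percentage points. For DET, quality of life and leakage scores the gain could be larger but cannot be quantified from the documents. These figures rest on SD 1.82, a two-sided 5% test, one score per period, a linear covariate and the assumed r. The documents do not establish bias in any planned contrast, and the change does not repair the two-stage carry-over rule.

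**What to change.** - **Section 7.1.1:** state that the baseline questions, V1 skin assessment, V1 questionnaires and V1 photo are completed before the randomisation number is drawn. The randomised product listed in Appendix 4 would be entered afterwards.
- **Section 11.1:** pre-specify that, whenever the first-period-only analysis is run, the V1 value of the same measure enters as a covariate for DET, quality-of-life and (where collected at V1) leakage scores. For weekly maximum itching, name the closest V1 skin item in advance and expect a smaller gain. Pre-specification matters, because choosing a covariate after a significant carry-over test would be open to criticism.
- **Optional:** add a 0–10 itching question before randomisation, which would give the primary endpoint a covariate on its own scale.

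The cost of the two core changes is a reordering of steps within one visit, one model term and one degree of freedom. No subjects or visits are added. The optional question adds one item.

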7.1.2. Visit calls

At the visit calls (week 2, 4 8 and 10 after visit 1), the Principal Investigator, or delegate, calls the subject to follow-up since the last visit/call. The PI will ask about the product, the clinical trial app, peristomal skin condition and stoma behaviour.

7.1.3. Product change

Every time the subject changes the full product or baseplate (2-piece users) they will use the clinical trial app to complete a questionnaire about skin condition, reason for change, use of accessories and ballooning. In addition, they will be asked to take photos of the peristomal skin and the back side of the removed product (leakage).

7.1.4. Safety

Safety (adverse events, device deficiencies) will be assessed at all visits, planned and unplanned phone calls.

7.1.5. Follow-up after the investigation

Subjects who do not have an ongoing AE are not followed termination of the investigation. For ongoing AEs at investigation termination, please see section 14.4. All subjects are encouraged to contact the Principal Investigator, if they experience problems that they believe are related to their participation. This is to ensure that any device-related events are documented and to safeguard the subjects' health.

7.1.6. Interview

In this investigation eight-twelve subjects in UK might be interviewed to include some [REDACTED]

[REDACTED] will be conducted as a telephone interview. The interviews, or relevant parts, will be tape recorded. It will not be possible to identify the subject from tape records. The subjects will be asked for consent, which include consent for the site personnel to forward the subjects contact information to the company performing the interview.

CONFIDENTIAL

7.2. Flow-chart

Table 3 chart showing the connection between visits and assessments. ¹ Investigator, or delegated personnel.

Assessment	Performed by	Visit 3		
		Inclusion visit (V0)	Test visit (V1)	Test visit (V2)
Oral information	Investigator ¹	X		
Written informed consent	Subject	X		
Check of inclusion and exclusion criteria	Investigator ¹	X		
Pregnancy test (urine sample) – females only	Subject	X		
Subject number allocated	Investigator	X		
Randomisation	Investigator	X		
Registration of Baseline data	Investigator ¹	X		
Introduction to Clinical Trial App	Investigator ¹	X	X	X
Assessment of subject wellbeing and compliance with CIP	Subject		X	X
Record change of product in Clinical Trial App, including photos and completion of questions related to change of product	Investigator		X	X
Photo of peristomal skin for assessment of changes in skin condition	Investigator		X	X
Complete visit questions in eCRF	Investigator ¹		X	X
Complete visit questions in Clinical Trial App	Subject		X	X
Investigational product hand-out according to randomisation	Investigator ¹		X	X
Subjects trained in how to prepare skin for the investigational product handed out, and how to use, handle, cut and store the product, according to IFU.	Investigator ¹		X	X
Hand-out remuneration and obtain signature	Investigator ¹ /subject		X	X
Arrange dates for the next test visit and calls	Investigation ¹		X	X
Inform Clinical Manager about scheduled visits	Investigation ¹		X	X
Adverse events incl. supplementary information	Investigation ¹		X	X
Device Deficiencies	Investigation ¹		X	X
Concomitant medication	Investigation ¹	X	X	X

CONFIDENTIAL

7.3. Case Report Forms

All assessments and observations throughout the investigation for each subject must be carefully recorded in an electronic CRF (eCRF) or an application (Clinical trial App) in a provided phone for each subject.

Assessments completed by the principal Investigator, or delegate, will be recorded in the eCRF. Questions completed by the subject at visits or at every product (1pc) or baseplate change (2pc) will be recorded in the Clinical Trial App. All data completed in the Clinical Trial App will be uploaded directly to the data base when the phone is on a network.

CRFs will be completed by the subject, and/or by the principal investigator, or delegate, who have signed the Site Personnel Signature and Delegation List and Clinical Investigation Training Log.

It is the responsibility of the Investigator that all data and observations are entered promptly and correctly.

